The WELL Study (Wellness Education for Liver Health Study): Reducing liver disease in genetically predisposed adults

Version: 12-2-21
HUM00154361

Principal Investigator
[name]

Methodology:

We will examine the feasibility and acceptability of our four-month, online, dietary intervention among 40 adults with NAFLD from a high-risk subpopulation (rs738409-GG and rs738409-CG).

Participant recruitment, liver clinic evaluation, and inclusion

and exclusion criteria. We have already identified candidates from the Michigan Genomics Initiative using their electronic medical records including outpatient laboratory values that are homozygous for *PNPLA3* rs738409 and have elevated liver-function tests (median alanine aminotransferase above 35 international U/L). They have already consented to be re-contacted and are motivated participants interested in further research. The clinical characteristics of eligible participants are given in **Table 2**.

We will contact the pool of potentially eligible participants by sending them a postcard describing the study, either in an envelope or with mailing information directly on the postcard. We may also send a follow up letter or flyer describing the study, in an envelope with either a handwritten or a typed address. Potential participants may also receive a phone call. Interested participants will fill out a screening survey; study team members will review their medical records for exclusions and elevated liver function tests. Participants that appear to meet inclusion and do not have exclusion criteria, based on their survey and medical chart, (**Table 3**) and agree to participate will be referred to our liver clinic to be evaluated to rule out other causes of elevated liver function tests (such as medications or high levels of alcohol intake).

Participants who are taking blood glucose-lowering medications will be considered

Table 2. Clinical Characteristics of Michigan Genomics Initiative rs738409-GGs with elevated ALT

Characteristic	rs738409 GG
Participants	363
Male Sex	162 (45%)
Age	48 [27–65]
BMI	32 [27–37]
ALT	49 [42–65]

Values are given as either median and interquartile range or as N (%).

Table 3. Inclusion and exclusion criteria.

Inclusion	Exclusion
Age > 18	Non NAFLD causes of elevated liver function tests
MRI with liver steatosis but not cirrhosis	Pregnant
English speaking and access to internet	Recent decompensation/hospitalization
Able to consent and follow directions	Weight loss medication or procedures planned
No physical limitations	Type 1 diabetes, cancer, heart failure, kidney failure, Cushing's syndrome
Physician approval to participate	Vegan, vegetarian, or other dietary restrictions
Rs738409 homozygote	Decompensated liver disease
Able to attend in-person appointments in Ann Arbor	Metal implants/inability to receive MRI

eligible for the trial. However, participants taking insulin will be excluded from participation. If the study team finds that recruitment is too slow and excluding insulin is too restrictive, participants taking insulin will be considered for enrollment. These participants will receive extra attention by study physicians in terms of medication management. See **Safety and medication management** section below.

Potentially eligible participants will complete a screening consent survey via Qualtrics. After consenting to screening activities, they will complete an online baseline survey concerning their general health and well-being, watch a short, informational video about the trial and answer several comprehension questions, and set up an appointment for a phone call with the study coordinator. Prior to the phone appointment, the study coordinator will send participants the full study consent via SignNow. During this appointment, the study coordinator will go over the full consent with participants, having them sign on SignNow when all questions are answered. After consenting, participants will schedule two appointments with the study coordinator. The first appointment will be a virtual visit with [name] at Michigan Medicine's Taubman Center liver clinic and the second will be a baseline liver MRI; participants will receive instructions to call and schedule their baseline MRI to ensure the schedulers have accurate safety information when scheduling the appointment. The virtual visit will be scheduled within one month of the phone call, the second will be scheduled two to four weeks after the first. Participants who elect to participate in the optional induced pluripotent stem (iPS) cell research will be asked to informally schedule a time to get their blood drawn at the Taubman blood draw clinic. This blood draw must take place at the hospital to ensure sample viability. Participants will choose a time on a weekday, ideally in the morning, within two weeks of their appointment with [name]. At the virtual visit, [name] will evaluate the full medical history and physical health. History will be evaluated for cardiovascular disease (angina, myocardial infarction, stroke, heart failure). If participants are not getting blood drawn for iPSC research, then they will proceed to a fasting blood draw at any MM Labs location (no appointment needed) within one to two weeks following this virtual visit. If participants are getting blood drawn for iPSC research and scheduled a time for their blood draw during their consent visit, then they will go to the Taubman Center blood draw clinic at the time of their appointment. A member of [name] team will either meet with participants when they arrive at the clinic to provide research tubes to the phlebotomist for the iPSC samples or will arrive immediately following the participant's blood draw to collect the samples. Blood tests will be drawn to assess (1) the cause of elevated liver function tests (complete blood count with differential; comprehensive metabolic panel; prothrombin time; C-reactive protein; erythrocyte sedimentation rate; hepatitis A, B, and C serologies; iron studies (iron level, iron binding capacity, percent transferrin saturation, ferritin); antinuclear antibodies; anti-LKM-1 antibodies, antimitochondrial antibodies; antismooth muscle antibodies; and alpha-1-antitrypsin levels), (2) diabetes (fasting glucose, fasting insulin, and hemoglobin A1c), and (3) dyslipidemia (serum lipid panel). Additionally, participants will have excess whole blood and serum drawn during their appointments. This serum (SST tube) will be transported to a lab in the University of Michigan's School of Public Health and tested for levels of an appetite suppressing hormone (growth differentiation factor: GDF15). For participants contributing blood for iPSC research, two tubes of whole blood (ACD solution A tubes or two CPT with sodium citrate tubes) will be drawn and transported to a lab within Medical Sciences Building II ([name] Lab). Participants may opt out of this step in the main study consent form. Also in the week following their virtual visit, participants must fill out an additional survey providing personal information, including their address (for mailed materials) and their primary care provider's name and phone number. Participants will also track their food for three days on the MyFitnessPal website or complete two 24-hour dietary recalls over the phone. The study team will reach out to the primary care providers of participants who have eligible blood tests. Primary care providers must approve their patient's participation before the subject is enrolled, within one month of first contact attempt. Primary care providers of participants who are taking blood glucose-lowering medications other than metformin will be advised that their patient may stop their medications as they begin the program to avoid risk of hypoglycemia. All primary care providers will be informed that their patient may reach out to them if they're experiencing symptoms or may need further medication adjustments.

[figure not shown]
Participants may be ineligible after their blood tests and virtual visit. If no other cause of elevated liver function tests is found except for NAFLD and the patient meets inclusion with no exclusion criteria, the patient will attend their second appointment at the main Michigan Medicine hospital to receive a baseline standard-of-care, clinical liver MRI-derived proton density fat fraction test, the gold standard for non-invasive measurement of both hepatic steatosis, fibrosis, and cirrhosis. Prior to this appointment, participants of childbearing potential will be mailed a urine pregnancy test. They'll be instructed to take this test the day of their MRI and to send a photo of the result to the study email (they can write their result if they're uncomfortable with a photo).

Participants with a positive test will be asked not to come in for their appointment and will not be eligible for the trial. At the second appointment, participants will complete an MRI screening with the technicians and may be ineligible if they are unfit for an MRI. Those whose MRI shows steatosis, mild fibrosis, and early cirrhosis (F1-4), will be invited into the trial, as these are the patients for whom we may be able to reverse fibrosis with intervention. (See **Figure 1** for the full flowchart of the study.) If participants are ineligible after completing their MRI, they will be compensated \$20 via Amazon gift card. The “psychological self-report” listed in Figure 1 for baseline and 4-month assessments includes questions concerning health-related quality of life,[1] dietary intake, physical activity,[2, 3] food cravings,[4] stress eating,[5, 6] dietary-based social support,[7] and hunger.[8]

Participants who are eligible after their MRI and have completed all other baseline measurements will be mailed a digital scale. Participants must weigh themselves on this scale within two weeks of receipt, before being enrolled in the trial.

Many of these measurements are standard of care for non-alcoholic fatty liver disease and will be charged to the participant’s insurance. Baseline and follow up virtual visits, the baseline clinical liver MRI, and all baseline and follow up blood tests (with the exception of the excess serum, excess whole blood, and the fasting insulin tests) will be charged to the participant’s insurance. Participants will be informed of this during the consent process and will be encouraged to check their plans to ensure they have coverage. The study will cover the costs of all other measurements and materials.

Figure 1. Flowchart of intervention study.

NAFLD standard of care. All participants will receive care at our NAFLD liver clinic; we will provide state-of-the-art care of and resources about NAFLD to all participants. An information packet will be provided to all participants at their baseline office visit that includes: 1) NAFLD disease information including diagnosis, clinical manifestations, natural history, and treatments; 2) NAFLD physical activity recommendations including walking programs and physical activity logs; 3) weight tracking logs; and 4) resources for exercise programs. [name], with gastroenterology fellows working with her, will provide all medical care. Adverse events will be routinely queried at each clinic visit and the study physicians will be on call in the case of an adverse event. All participants will be taught a VLCD diets using our validated online program.

Participants will have a baseline virtual visit with [name] in the liver clinic and, if they appear eligible, they will come back for an MRI. After all baseline measurements are completed and if participants are still eligible, they will be enrolled in the 4-month online program. This program will include weekly lessons, mailed materials, and the support of a dietary coach. Details are outlined below:

VLC Diet. Participants will be encouraged to eat a VLCD, the same one [name] has found effective in her previous research,[9] and to reduce carbohydrate intake to between 20-35 non-fiber grams of carbohydrates a day with the goal of achieving nutritional ketosis, defined as a positive urine dipstick (Bayer Ketostix), which measures the ketone acetoacetate. A VLCD restricts carbohydrate intake to a point that induces a low level of ketone production. Nutritional ketosis may indicate that insulin levels are reduced to a level that the body is using fat as the key source of energy, turning on fat burning (lipolysis).¹⁵ When this occurs, some fats are turned into ketones, which serve as a readily used fuel.¹⁶ This is a commonly used approach,[10, 11] and results from our pilot[9] and other studies[12-15] provide empirical support for this type of diet.[16]

Support. As changing a diet can be complex, several sessions are necessary to comprehensively and effectively teach a new way of eating. All participants will be e-mailed links every week for 16 weeks that connect them to a) a short survey to assess intervention-related behavioral adherence and health concerns, b) a short video to teach the topics, c) downloadable handouts distributed online to accompany the videos, and d) links to external resources on the web pertaining to the week's information. As some participants prefer not to watch videos, the transcripts of the embedded videos will be provided as well, in an easy-to-read downloadable format. The lessons can be watched and read whenever is convenient and take about 10 to 30 minutes to complete. As coaches have been found to be effective additions to behavioral interventions,[17] if participants in the groups have questions, they will be able to contact a coach in order to receive prompt replies. Coaches will be trained, and coaching quality will be monitored for fidelity to our coaching manual.

All participants will be provided with extra support tools. These will be taught with a weekly short video, downloadable handouts, and links to external resources. Below, we describe the justification for the behavioral support we include.

a) Training in positive affect and mindful eating. To adhere to a new diet, participants need to cope effectively with inevitable stressors. According to the revised Stress and Coping Theory[18, 19] positive emotions serve as a psychological “time-out” from the upset caused by stress and improve the motivation to adaptively cope with stress.[20] Moreover, our intervention aims to help participants better enjoy and savor their food. Hedonic theories of behavior propose that people will be more likely to continue doing behaviors they enjoy,[21] and previous research shows a connection between greater eating plan satisfaction and better eating plan adherence.[22, 23] Those who eat as a way to cope with their emotions tend to regain more weight after successful weight loss.[24, 25] The psychological causes of emotional eating may involve poor awareness of internal physiological states and differentiation between hunger cues and emotional arousal.[26-28] To counteract the tendency to eat when stressed, we will draw on Mindfulness-Based Eating Awareness Training (MB-EAT),[29, 30] which includes exercises to increase the awareness of the triggers of overeating, internal cues that signal hunger and fullness, and ways to cultivate healthier alternative behavior. We will teach these diet- and health-focused skills; how they are expected to help; research supporting them; and suggestions for practicing them.

b) Dietary self-monitoring using a free online or mobile application. We will ask participants to track their diet using a free online and mobile application, MyFitnessPal (which our participants have found easy to use, has a wide variety of foods in its database, and has over 150 million users). Previous participants have nearly unanimously enjoyed using this application. We will encourage dietary tracking daily for the first few weeks of the program, tapering to at least a few days a week by about week 4. Participants will first be asked to track their regular eating pattern with MyFitnessPal before they begin the program (during their enrollment process). Participants will be encouraged but not required track their eating throughout the intervention to support them in making dietary changes and follow the very low carb diet. Finally, participants will be asked to track for three days near the end of the intervention for assessment of dietary adherence.

c) Body weight self-monitoring using a digital scale. At the start of their 4-month program, participants will be mailed a scale. We will ask participants to track their body weight weekly with this scale, which is easy

to use and connects via a cellular network. Because it connects via its own cell network, participants do not have to set up any passwords, simplifying ease of use. We will use this information to monitor participant success and tailor coaching support.

d) Mailed materials. At week 1, week 6 and week 11, we will mail participants lay-press cookbooks to help with increasing variety in their diet. This approach has been popular with our previous participants. Although meal replacements have been studied, and are generally found to be helpful for weight loss,[31, 32] this cookbook approach is novel. Also at week 1, participants who are taking glucose-lowering medication (other than metformin) will be sent a glucose-monitoring device via Amazon, so that they may self-monitor their glucose.

e) Text messages. Reminders about targeted behaviors are tied to greater behavioral adherence.[33] Thus, to encourage the adoption and maintenance of the new intervention-related behaviors, participants will be sent text messages to give them feedback as well as to motivate, educate, and remind them about the targeted behaviors and skills.[34] Thus, as [name] has done in her previous research, we will send automatic, motivational, and educational skill-relevant messages about 5 times a week to participants.[35, 36] Although most previous participants enjoyed the messages, participants have the option to opt out of text messages.

Safety and medication management. Participants will be asked in a weekly survey about health symptoms or adverse events they've experienced and to report any medication changes they've made. Participants who report symptoms will be reached by email as soon as possible by the study coordinator or diet coach. Participants may be called if the health event seems urgent or severe. For severe or long lasting symptoms, participants will be encouraged to reach out to their primary care physician. Participants who are taking some blood glucose-lowering medications (metformin, DPP-4s, GLP-1 agonists, and Thiazolidinediones (TZDs)) will continue their medications as normal. Participants taking all other glucose-lowering medications will be asked to stop taking these medications at the start of the trial (PCPs will be informed of this change when participants begin the trial). All participants will be asked in the aforementioned weekly survey about their highest and lowest fasted and postprandial (2 hours after eating) blood glucose levels over the previous week. If participants report low glucose (fasting below 70 mg/dL or postprandial below 110 mg/dL), they should reach out to their physician and follow self-management guidelines (sent to them as part of week 1's intervention materials). If participants report more than two weeks of high blood glucose (180 mg/dL), [name] [name] will reach out to participants via email or phone about management and reach out to participant PCPs.

Outcomes and analyses. After 16 weeks of the VLCD program, participants will complete a series of follow up measurements. Participants will complete a virtual follow up office visit, a follow up self-report survey, track their food, weigh themselves on the scale we sent them, take an at-home urine pregnancy test (if of childbearing potential), and return for a MRI-derived proton density fat fraction test. All final measurements should be completed within 4 weeks of completion of the program. Additionally, the second MRI will be conducted on research machines and charged to the study. Participants will also have a fasting blood draw. Follow up blood tests will include: complete blood count with differential, comprehensive metabolic panel, prothrombin time, fasting glucose, hemoglobin A1c, fasting insulin, and a serum lipid panel.

Statistical Design:

Based on a previous, small, short-term trial without genetic biomarkers,[1] we expect patients enrolled in this program to lose 12% of their liver fat with a standard deviation of 6%. With a one-sample Wilcoxon test, this sample is 99% powered to detect such a decrease in MRI-derived fat fraction at $\alpha = 0.01$. Extrapolating from the epidemiological association of the rs738409-GG genotype with fatty liver in insulin-resistant patients,[2] the benefit in this group may be twice as high as in the general population (24%); if so, we would likewise be 99% powered to detect a reduction *significantly greater than* 12% at $\alpha = 0.01$.

One-sample Wilcoxon tests will likewise be used for post-program vs. baseline insulin resistance and body weight as secondary outcomes. We do not anticipate significant fibrotic differences after 4 months on this intervention, but will report pre-post liver fibrosis values. Baseline and post-program semi-structured interviews, as in Aim 1, will be used to assess satisfaction, adherence and dropout.

1. Reeve, B.B., et al., *Psychometric evaluation and calibration of health-related quality of life item banks: plans for the Patient-Reported Outcomes Measurement Information System (PROMIS)*. Medical care, 2007. **45**(5): p. S22-S31.
2. Craig, C.L., et al., *International physical activity questionnaire: 12-country reliability and validity*. Medicine & Science in Sports & Exercise, 2003. **35**(8): p. 1381-1395.
3. Kiernan, M., et al., *The Stanford Leisure-Time Activity Categorical Item (L-Cat): a single categorical item sensitive to physical activity changes in overweight/obese women*. International journal of obesity (2005), 2013. **37**(12): p. 1597.
4. Dalton, M., et al., *Preliminary validation and principal components analysis of the Control of Eating Questionnaire (CoEQ) for the experience of food craving*. European journal of clinical nutrition, 2015. **69**(12): p. 1313.
5. Tsenkova, V., J.M. Boylan, and C. Ryff, *Stress eating and health. Findings from MIDUS, a national study of US adults*. Appetite, 2013. **69**: p. 151-155.
6. Burgess, E., et al., *Profiling motives behind hedonic eating. Preliminary validation of the Palatable Eating Motives Scale*. Appetite, 2014. **72**: p. 66-72.
7. Norman, G.J., et al., *Reliability and validity of brief psychosocial measures related to dietary behaviors*. International Journal of Behavioral Nutrition and Physical Activity, 2010. **7**(1): p. 56.

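### The glucose meter goes out only at week 1, and nothing ensures it is in hand before the diet and any drug stop begin: a minor safety gap that is cheap to close

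*Combined protocol and SAP*

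**What the plan says.** Item d) Mailed materials sets the timing of the meter: "Also at week 1, participants who are taking glucose-lowering medication (other than metformin) will be sent a glucose-monitoring device via Amazon". The stated purpose is self-monitoring.

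Safety and medication management divides the drugs into two sets. Users of four classes carry on: "metformin, DPP-4s, GLP-1 agonists, and Thiazolidinediones (TZDs)) will continue their medications as normal". For the rest, "Participants taking all other glucose-lowering medications will be asked to stop taking these medications at the start of the trial". The recruitment section gives the reason. Primary care providers of patients on drugs other than metformin "will be advised that their patient may stop their medications as they begin the program to avoid risk of hypoglycemia".

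Monitoring is weekly. "Participants will be asked in a weekly survey about health symptoms or adverse events", and the same survey asks every participant for the "highest and lowest fasted and postprandial (2 hours after eating) blood glucose levels over the previous week". A participant who reports a fasting value under 70 mg/dL or a postprandial value under 110 mg/dL should contact a physician and follow self-management guidelines, which also arrive with the week 1 materials.

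The scale is handled differently in the recruitment section: "Participants who are eligible after their MRI and have completed all other baseline measurements will be mailed a digital scale", and then "Participants must weigh themselves on this scale within two weeks of receipt, before being enrolled in the trial". Item c), on body weight self-monitoring, instead has the scale mailed when the 4-month program starts.

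**The concern.** The first days of the program are when carbohydrate intake is meant to fall to 20-35 non-fiber grams a day and when some participants stop a drug. The plan singles out users of drugs other than metformin for home glucose readings, and its low-glucose instruction can be acted on only by someone who has a reading. Yet the meter is sent in the same week as the change, with no check that it has arrived. Following the plan as written, a participant could begin without a study meter and without the guidelines on what to do about a low value. What is at stake is a small amount of early safety monitoring. The efficacy analysis is not affected.

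**Working it through.** The protocol states no figure on this point, so the check is a comparison of its timing statements.

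**1. Who gets a meter, and what happens to their drugs** (Mailed materials; Safety and medication management)

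| Participant's glucose-lowering drugs | Study meter | Drug at start | Asked weekly for glucose values |
|---|---|---|---|
| None, or metformin only | No | Unchanged | Yes |
| DPP-4s, GLP-1 agonists or TZDs | Yes, sent at week 1 | Continued | Yes |
| Any other class (insulin excluded by default) | Yes, sent at week 1 | Stop requested | Yes |

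The second and third rows form the meter group. Its size is not given. The planned enrolment of 40 (Methodology) is a ceiling, not an estimate.

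**2. Order of events.** The drug stop is set at the start of the trial, and the recruitment section ties it to beginning the program. The meter is sent at week 1. Let S be the day the participant starts the diet or stops a drug, and R the day the meter is received and working. Days without study-supplied readings = max(0, R − S). Neither S nor R can be fixed from the protocol:
- no delivery time is given;
- the order of days within week 1 is not stated;
- lessons may be taken at the participant's convenience (Support), so the diet's first day is open.

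The gap is zero if R falls on or before S, and positive otherwise. Nothing in the text forces R to come first.

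**3. Is there a check elsewhere?** None was found. Primary care approval, the baseline blood draw, the MRI and a weigh-in all precede enrolment, but no step concerns the meter.

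**4. What works without a meter.** Five things do: the drug stop, which is the plan's own measure against hypoglycemia; the default exclusion of insulin users; primary care approval; the weekly question on symptoms; and on-call study physicians (NAFLD standard of care).

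**5. What does not.** The low-glucose instruction needs a reading. Those left relying on it are participants who continue DPP-4s, GLP-1 agonists or TZDs, and anyone whose requested stop is late or not carried out. The protocol gives no rate of low glucose for either.

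**6. High glucose.** Study contact follows more than two weeks of readings at 180 mg/dL, so this rule cannot be met in week 1 with or without a meter. A late meter could postpone it by at most R − S days.

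**7. Analysis.** The outcomes under Statistical Design do not use home glucose readings. The glucose, insulin and hemoglobin A1c measurements come from blood draws. Sample size and power are untouched.

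**The case against.** The strongest reply is that no gap has been shown. The meter may arrive before a participant changes anything, some participants may already own one, and a text silent on a delivery step is not in error. This stands in part: it rules out calling the gap a proven delay. It does not remove the point, because the plan does fix a dispatch time, and that time allows the meter to come second.

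A reader might go further and infer that patients at risk of hypoglycemia go unprotected in week 1. The documents do not support that. The drugs outside the four continued classes are stopped for this very reason, insulin users are excluded by default, and symptoms are asked about each week.

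A reader might also want to state the loss as a share of week 1 or of the 16 weekly reports. Any such figure only restates an assumed delay. If delivery took 1 to 7 days and the diet began on the day of dispatch, the gap would be 1 to 7 days, but the protocol supports neither assumption and sets no upper limit.

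Three further objections have force:
- The survey asks all participants for glucose values although only some receive a meter, so blank answers are already expected. A blank in week 1 is not in itself a failure of the plan.
- The scale is a weak precedent. Body weight is a secondary outcome compared with baseline, so a weight before the program is needed for analysis; the meter measures no listed outcome. The scale shows that a check before enrolment is workable, not that the plan is inconsistent in leaving the meter without one.
- Sending the meter with the scale would gain little if the scale goes out at program start, as item c) says. The fix must therefore be stated in terms of enrolment.

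**Conclusion.** The point holds as a cheap, minor safety improvement. The meter's timing is a dispatch rule, and no section requires the device to be in hand before the diet and any drug stop begin. The group the plan chose for self-monitoring may therefore lack study-supplied readings for an unknown number of first days. Confidence is moderate.

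The size cannot be given. It depends on delivery time, the number in the meter group and their rate of low glucose, none of which the protocol states. The low grade rests on insulin users staying excluded and on requested drug stops being carried out. If slow recruitment leads the team to admit insulin users, as the recruitment section allows, the point matters more: closer physician oversight of medication is promised for them, but the meter timing is unchanged.

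**What to change.** Amend item d) Mailed materials for participants on glucose-lowering drugs other than metformin:

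- Send the meter, together with the low-glucose self-management guidelines, after the eligibility MRI and before enrolment. Any supply route will do.
- Have the coordinator confirm receipt and one working reading before the participant begins the diet or stops any drug.
- Do not define the timing only as being with the scale. Separately, align the scale sentence in item c) with the recruitment section, which requires a weigh-in before enrolment.

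No drug rule, glucose cut-off, endpoint or sample size changes. The devices are the same. The costs are a few meters sent to people who then do not enrol, one more start condition for the coordinator to track (for at most 40 people), and a short wait for anyone whose delivery is late. The change should in any case be in place before an insulin user is enrolled.
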